4.2 Scientific Rationale for Study Design

This is a Phase 3, single-arm, multi-center, open-label study to assess the contraceptive efficacy and safety of the NOMAC-E2 COC. The study has been designed to meet the regulatory requirements for registration within the US in accordance with the 2019 FDA Guidance Establishing Effectiveness and Safety for Hormonal Drug Products Intended to Prevent Pregnancy (19) and it has also taken into account multiple interactions between the FDA and the Sponsor (ie, incorporation of FDA's recommendations into the study design and assessments).

The study has a duration of 1 year (thirteen 28-day cycles) and primarily aims to establish the contraceptive efficacy of the NOMAC-E2 COC in women aged 14 to 35 years (inclusive), at risk of pregnancy. The assessment of efficacy is based on the point estimate and the upper bound of the corresponding 95% CI for the PI. To be considered a very effective COC, the upper bound of the 95% CI for the PI should not exceed 5 in an adequately designed and conducted study. The anticipated exposure of >14,000 cycles at risk in 1,878 participants expected to complete 1 year of treatment (thirteen 28-day cycles) has been calculated to provide a PI conforming to this requirement (see Section 9.4.2 for additional information). In addition to the post-marketing data, the results from this study will also provide additional support to the clinical safety of the NOMAC-E2 COC. This study is open label and does not have a comparator arm, as this is not needed to meet regulatory requirements for registration.

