1.1 Synopsis

Protocol Title: A Phase 3, Open-label, Multi-center, Single-arm Study to Assess Contraceptive Efficacy and Safety of the Nomegestrol Acetate + 17 β -estradiol Combined Oral Contraceptive (OG-8175A) in Premenopausal Females Aged 14 to 35 Years (Inclusive).

Short Title: Contraceptive Efficacy and Safety of NOMAC-E2 Combined Oral Contraceptive
Rationale:

Nomegestrol Acetate + 17 β -estradiol (NOMAC-E2; OG-8175A) is a monophasic combined oral contraceptive (COC) containing nomegestrol acetate (NOMAC), a nor-progesterone-derived progestogen, and 17 β -estradiol (E2), an estrogen that is identical to the predominant endogenous human estrogen (E2). NOMAC is a highly selective progestogen derived from, and structurally similar to, the naturally occurring steroid hormone, progesterone. NOMAC has a strong affinity for the human progesterone receptor and has strong anti-gonadotropic activity, moderate anti-androgenic activity, and is devoid of any estrogenic, androgenic, glucocorticoid, or mineralocorticoid activity. The estrogen contained in NOMAC-E2 is 17 β -estradiol, an estrogen identical to the predominant endogenous human estrogen. This estrogen differs structurally from the estrogen ethinylestradiol (EE) used in other combined hormonal contraceptives (CHC) by the lack of the ethinyl group in the 17- α position.

Phase 2 and 3 clinical studies have shown that NOMAC-E2 has robust contraceptive efficacy, a stable vaginal bleeding profile, and a good overall safety and tolerability profile, as compared with the COC containing drospirenone (DRSP) 3.0 mg and EE 30 μ g. NOMAC-E2 has less pronounced effects on metabolic parameters than the levonorgestrel (LNG)-EE 150/30 μ g COC. NOMAC-E2 was first registered in July 2011 and is currently registered and marketed in over 50 countries worldwide, including the member states of the European Union, the United Kingdom, and Australia.

[Redacted content]. Mainly, this is a single-arm clinical study that will include the following:

- A total of 1,878 participants to yield: a) >1,000 participants who will complete 1 year (thirteen 28-day cycles) of treatment and b) >16,500 28-day cycles of exposure to assess the safety and contraceptive efficacy of NOMAC-E2.
- The demographic characteristics (age, weight, body mass index [BMI; see exclusion criterion #15], racial distribution, etc.) as per inclusion/exclusion criteria are targeted to be representative of females of childbearing potential in the US.

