A total of 2,680 fertile premenopausal women aged 14 to 35 years (inclusive) will be screened to achieve about 1,878 being allocated to study treatment. Over 1,000 total participants are expected to complete 1 year of treatment (13 cycles).

Treatment Groups and Duration:

All participants will receive the NOMAC-E2 COC. Participants will take one tablet of study drug per day for a period of thirteen 28-day treatment cycles. Each 28-day treatment cycle consists of 24 days of active medication intake, followed by 4 days of placebo. The total duration of study participation will be up to 60 weeks, which includes a Pre-treatment Period of maximally 6 weeks, a Treatment Period of 52 weeks, and a Follow-up Period of 2 weeks after the last intake of study drug.

Statistical Methods:

A PI of 3.0 is assumed for the NOMAC-E2 COC, which is similar to the values observed for low dose COCs such as LoLoestrin™ (norethindrone/EE) and Quartette™ (LNG/EE). This is considered to be a conservative estimation, as previous clinical study data suggest that the NOMAC-E2 COC is associated with a lower PI than higher dosed COCs such as DRSP/EE 3.0 mg/30 µg (Yasmin™), while recent large scale observational study data suggest that the NOMAC-E2 COC may also have a PI much lower than the LNG/EE 150/30 µg COC (eg, Levora).

(see Section 9.2).

Primary and Secondary Efficacy Analyses:

Contraceptive Efficacy:

The estimated PI with associated 95% CI will be calculated for the primary and secondary contraceptive efficacy endpoints of on-treatment pregnancies PI_{at-risk}, PI_{perfect use}, and PI_{typical use}. The PIs will be estimated by means of the maximum likelihood estimate of the mean parameter in a Poisson distribution. The PIs will also be summarized by BMI subgroup.

A time-to-pregnancy analysis under at-risk, perfect use, and typical use circumstances will be performed using the Kaplan-Meier approach. Participants who do not become pregnant will be censored at the last day of the on-treatment period. The cumulative probabilities of in-treatment pregnancies after thirteen 28-day treatment cycles will be estimated.

Bleeding Profile:

The main vaginal bleeding endpoints in the Cycle Control Analysis are:

- Proportion of participants who experienced unscheduled bleeding-spotting
- Proportion of participants who experienced absence of scheduled bleeding-spotting
- Proportion of participants who experienced no scheduled or unscheduled bleeding-spotting at all

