Post-marketing surveillance data collected from more than 4 million WY of exposure have confirmed the favorable benefit-risk profile of NOMAC-E2.

████████
████████
████████
████████

Mainly, this is a single-arm clinical study that will include the following:

- A total of 1,878 participants to yield: a) >1,000 participants who will complete 1 year (thirteen 28-day cycles) of treatment and b) >16,500 28-day cycles of exposure to assess the safety and contraceptive efficacy of NOMAC-E2.
- The demographic characteristics (age, weight, body mass index [BMI; see exclusion criterion #15], racial distribution, etc.) as per inclusion/exclusion criteria are targeted to be representative of females of childbearing potential in the US.
- The study assessments are designed to capture all information related to the concomitant use of condoms and other forms of contraception during the Treatment Period.

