9.2 Sample Size Determination

9.2.1 Main Analysis

A PI of 3.0 is assumed for the NOMAC-E2 COC, which is similar to the values observed for low dose COCs such as LoLoestrin (norethindrone/EE) and Quartette (LNG/EE). This is considered to be a conservative estimation, as previous clinical study data suggest that the NOMAC-E2 COC is associated with a lower PI than higher dosed COCs such as DRSP/EE 3.0 mg/30 µg (Yasmin), while recent large scale observational study data suggest that the NOMAC-E2 COC may also have a PI much lower than the LNG/EE 150/30 µg COC (eg, Levora).

(19).

[figure not shown]
A summary of the number of at-risk cycles and number of treated participants required is presented in [Table 9](#) for different scenarios of expected PIs ranging between 2.4 and 3.4 in order to achieve 80%, 85%, or 90% power, respectively.

Table 9 Number of at-risk Cycles and Number of Treated Participants Required Depending on Expected PI to Achieve an Assumed 80%, 85% or 90% Power

PI Expected	Power ^a (%)	Number of At-risk Cycles	Number of Treated Participants
2.4	80	5557	731
2.4	85	5903	776
2.4	90	7060	928
2.6	80	6847	900
2.6	85	7212	948
2.6	90	8307	1092
2.8	80	8417	1107
2.8	85	8825	1160
2.8	90	9890	1300
3.0	80	10717	1409
3.0	85	11643	1531
3.0	90	12708	1671
3.2	80	12695	1669
3.2	85	14941	1964
3.2	90	16481	2167
3.4	80	16469	2165
3.4	85	18629	2449
3.4	90	20997	2760

Abbreviations: CI=confidence interval; PI=Pearl Index.

a. The “probability of success” or “power” represents the probability that the upper CI limit of the PI will be no larger than 5.0, under the various assumptions of the PI and that the number of pregnancies follow a Poisson distribution. The power was derived, based on formula (14) and exact Poisson probabilities, computed in the R software.

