### 3.2. CHANGES TO ANALYSIS FROM PROTOCOL

Only safety analyses will be performed for this study. Efficacy and PK analyses will not be performed.

Consequently, the Safety Analysis Set (SAF), Allocated Participants Set (APS), and Multiple Enrollment Set (MES) as described in [Section 5](#) will be used.

The protocol (footnote to Table 11) specifies that laboratory and vital will be analysed up 28 days after last tablet intake; however, the protocol also specifies that the follow-up visit occurs 14 days (+5 days) after the last tablet. Therefore, this is now corrected in the footnote of Table B of the SAP.

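### Does the sample size rest on 1,878 one-year completers, and are the powers in Table 9 wrong?

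*Protocol*

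**What the plan says.** Section 4.2 of the protocol states the efficacy requirement (the upper bound of the 95% CI for the Pearl Index should not exceed 5) and supports it with "The anticipated exposure of >14,000 cycles at risk in 1,878 participants expected to complete 1 year of treatment (thirteen 28-day cycles").

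Other sections describe the same 1,878 differently:

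- Synopsis, Number of Participants: 2,680 women "will be screened to achieve about 1,878 being allocated to study treatment", and "Over 1,000 total participants are expected to complete 1 year of treatment (13 cycles").
- Synopsis, Rationale: "A total of 1,878 participants to yield: a) >1,000 participants who will complete 1 year (thirteen 28-day cycles) of treatment".
- Section 2.1: the same yield, together with ">16,500 28-day cycles of exposure to assess the safety and contraceptive efficacy of NOMAC-E2".

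For the sample size, Section 9.2.1 says "A PI of 3.0 is assumed for the NOMAC-E2 COC". Table 9 lists at-risk cycles and treated participants for Pearl Indices of 2.4 to 3.4 at 80%, 85% and 90% power. Its footnote says that power "represents the probability that the upper CI limit of the PI will be no larger than 5.0", derived from a formula (14) and exact Poisson probabilities. The readable text neither prints that formula nor names the type of interval.

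The SAP, written after early termination, states in Section 3.2: "Efficacy and PK analyses will not be performed".

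**The concern.** Two things look wrong.

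First, the sentence that justifies the exposure appears to assume no dropout, while the rest of the protocol expects little more than half of the participants to finish (1,000/1,878 = 53% as a lower bound). If the 14,000 at-risk cycles had been worked out from 1,878 completers, the trial could fall short of the exposure needed to hold the upper limit at 5.

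Second, a reader who recomputes Table 9 with the most familiar choice, an exact two-sided 95% Poisson interval, finds every row below its label. If that were the interval intended for the Pearl Index, the stated powers would be too high by 1 to 8 percentage points.

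**Working it through.** **1. Which count do the 14,000 at-risk cycles fit?**

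Inputs: 1,878 participants, more than 14,000 at-risk cycles (Section 4.2); more than 1,000 completers, more than 16,500 cycles (synopsis, Section 2.1); 12,708 at-risk cycles for 1,671 treated participants (Table 9, Pearl Index 3.0, 90%).

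- If all 1,878 completed: 1,878 × 13 = 24,414 cycles, which is 24,414/16,500 = 1.48 times the planned exposure.
- Planned exposure per participant: 16,500/1,878 = 8.8 cycles, well short of 13.
- Check of the planned figures at their lower bounds: 1,000 × 13 = 13,000 cycles from completers leaves 3,500 for the other 878, or 4.0 cycles each. The two figures are consistent with dropout.
- At-risk cycles per participant in Section 4.2: 14,000/1,878 = 7.45.
- At-risk cycles per treated participant in Table 9: 12,708/1,671 = 7.605. All 18 rows lie between 7.60 and 7.61.
- Table 9's ratio applied to the planned number: 1,878 × 7.605 = 14,282, which agrees with more than 14,000.

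So the exposure figure matches 1,878 treated women with dropout and not-at-risk cycles already allowed for. Only the descriptive phrase attached to 1,878 is wrong.

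**2. Table 9, row for Pearl Index 3.0 and 90% power**

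Woman-years = 12,708/13 = 977.5. The ceiling of 5 per 100 woman-years becomes 5 × 977.5/100 = 48.88 pregnancies. The expected count is 3.0 × 977.5/100 = 29.33. Power is P(X ≤ c) for a Poisson count with that mean, where c is the largest count whose upper limit does not exceed 48.88.

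| Limit assumed | Largest passing count (limit) | Next count (limit) | Power |
|---|---|---|---|
| Exact two-sided 95% | 35 (48.68) | 36 (49.84) | 87.1% |
| Two-sided Wald 95%, x + 1.96√x | 36 (47.76) | 37 (48.92) | 90.4% |
| Exact one-sided 95% | 37 (48.68) | 38 (49.81) | 93.0% |

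The readings differ by one pregnancy each, and each pregnancy is worth about three points. The Wald limit returns this row's label.

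**3. All 18 rows by the same method**

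| Limit assumed | 80% rows | 85% rows | 90% rows | Rows within 2 points of label |
|---|---|---|---|---|
| Exact two-sided | 75.4–79.0 | 79.1–83.5 | 82.0–87.5 | 5 |
| Mid-P two-sided | 76.6–83.2 | 79.1–86.5 | 86.9–89.1 | 10 |
| Wald two-sided | 82.7–90.2 | 86.6–91.3 | 90.0–92.9 | 5 |
| Exact one-sided | 84.5–87.5 | 85.8–89.7 | 90.7–93.7 | 3 |

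Under Wald every row reaches its label after rounding (the lowest margin is 89.98 against 90). Some rows overshoot: 5,557 cycles labelled 80% gives 90.2%. Score and Byar limits give the same values as the exact two-sided limit. No limit tried returns the whole table.

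**4. Power at the planned size, Pearl Index 3.0**

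| At-risk cycles | Exact two-sided | Wald |
|---|---|---|
| 14,000 | 89.4% | 94.3% |
| 14,282 | 90.2% | 94.7% |

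**The case for a change.** The case for acting is this. The Section 4.2 sentence is current protocol text, fully readable, and contradicted by the synopsis and Section 2.1. It sits where the protocol argues that the size meets the efficacy requirement, and correcting it would cost one line. Table 9 is the only readable support for the power, and a reader cannot tell whether 90% means 87%, 90% or 93%. The choice matters more at less favourable rates: with 14,282 at-risk cycles and a Pearl Index of 3.4, power is 70.4% under exact limits and 80.3% under Wald, and the readable table has no row for 1,878. Moreover, in every row the smallest count that reaches the labelled power has an exact 95% upper limit of 5.02 to 5.24.

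The wording conflict stands, and so does the failure to reproduce Table 9 from the public text. The rest does not carry the argument. The 5.02 to 5.24 result evaluates the counts with the exact limit, so it repeats that assumption instead of testing it; under Wald the same counts have upper limits of 4.69 to 4.95. Part of the Section 9.2.1 text before the table is missing from the public copy, and the interval and the reasoning for 1,878 may well be there. What is missing for that reason cannot be counted as missing from the plan.

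**Conclusion.** No change is needed. The Section 4.2 phrase is a clerical slip: it attaches the completion expectation to all 1,878 participants when the design expects more than 1,000 of them to complete. The exposure figure beside it fits the treated number (7.45 against 7.6 at-risk cycles each), and anyone using the synopsis, Section 2.1 or Table 9 works from the right counts.

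For Table 9, the finding is limited to non-reproducibility from this copy. An exact two-sided interval would put the labels 1 to 8 points too high; a Wald or one-sided limit would make them met or conservative. The documents do not settle which applies, so no error is shown.

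Neither point affects a result. At the assumed Pearl Index of 3.0 the planned size gives about 89% to 95% power under the limits tried, and after early termination the Pearl Index will not be analysed. These figures assume Poisson counts, 13 cycles per woman-year and, for 14,282 cycles, Table 9's ratio of at-risk cycles to treated participants.

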4.3 Justification for Dose

The NOMAC-E2 COC active tablets contain 2.5 mg NOMAC and 1.5 mg E2 and will be used in a 24/4 regimen, ie, 28-day cycles with 24 days of active tablet intake followed by 4 days of placebo tablet intake. The doses and regimen have been selected based on providing strong ovulation inhibition and good cycle control and are currently the marketed approved dose and regimen in countries wherein NOMAC-E2 is approved.

4.4 End of Study Definition

The end of the study is defined as the date of the last visit of the last participant in the study.

A participant is considered to have completed the study if she has completed all phases of the study, including the last scheduled procedure indicated at the EOS Visit shown in the Schedule of Activities (SoA); Section 1.3.

5.0 STUDY POPULATION

Prospective approval of protocol deviations to eligibility criteria, also known as protocol waivers or exemptions, is not permitted.

5.1 Inclusion Criteria

Participants are eligible to be included in the study only if all of the following criteria apply:

Demographics

1. Is a postmenarcheal, premenopausal female, aged 14 to 35 years (inclusive) at the time of informed consent signing.
2. Is at risk for pregnancy (heterosexual vaginal intercourse at least once a month and not sterilized), with a partner who is not known to be subfertile, sterilized, or infertile.
3. Does not desire a pregnancy within 1 year following screening and is not intending to use any other form of contraception (eg, condoms) including withdrawal.
4. Is in good physical and mental health, based upon the medical judgment of the Investigator.
5. Has a history of regular menstrual cycles of 21 to 35 days prior to the use of any hormonal contraceptive.
6. Is able and willing (in the opinion of the Investigator) to adhere to all required study procedures, including study visits and e-Diary entries, and not planning to relocate during the study (such that the participant would not be able to continue participation at the study site).

Note: Participants are eligible to participate in the study, if they have demonstrated capability to independently complete the e-Diary and have completed the questions related to bleeding at least 6 out of 7 days of the last week preceding treatment allocation (V2).

Informed Consent

7. The participant (or legally acceptable representative, if applicable) provides written informed consent (and assent, if applicable) for the study.

5.2 Exclusion Criteria

The participant is excluded from the study if the participant:

Recent or Current Pregnancy

1. Has a known or suspected pregnancy.

Note: A negative serum β -hCG test at V1 and a negative urine pregnancy test at V2 are required for a participant to be eligible in this study.

2. Has a history of subfertility or infertility.
3. Has not had at least 2 normal menstrual cycles following a recent pregnancy regardless of gestational age.

4. Is breastfeeding or has been breastfeeding within 2 months prior to start of study drug.

Gynecologic Conditions

5. Has a known human immunodeficiency virus (HIV) infection.

Note: This condition requires the use of condoms, which is not allowed per protocol.

6. Has untreated gonorrhea, chlamydia, or trichomonas.

Note: These conditions require the use of condoms, which is not allowed per protocol.

Participants may be rescreened 3 weeks after completing treatment for these conditions if not at risk for reinfection as deemed by the Investigator.

7. Has no documented normal PAP test within the timeline of current standard of care guidelines or has a significantly abnormal PAP test at Screening (V1) (ie, ASC-H, low grade squamous intraepithelial lesion, high grade squamous intraepithelial lesion, atypical glandular cells [any type], squamous cell carcinoma, or adenocarcinoma [in situ or invasive]). The presence of high-risk human papillomavirus (HPV), regardless of PAP result, is exclusionary.

Note: The presence of atypical squamous cells of undetermined significance (ASCUS) will require HPV reflex testing; ASCUS in an HPV-negative patient is not exclusionary.

8. Has had any unexplained abnormal vaginal bleeding or abnormal vaginal bleeding attributable to underlying pathology (ie, cervical/endometrial polyp, uterine fibroids, endometriosis, etc.) which has not been treated/resolved.

Cardiovascular Risks and Disorders:

9. Has a presence or history of VTE (ie, deep vein thrombosis, pulmonary embolism), a history of arterial thrombotic or thromboembolic events (ATE) (ie, myocardial infarction, stroke, or peripheral arterial disease), or a history of transient ischemic attack, angina pectoris, or claudication.

10. Is at a higher risk of VTE due to major surgery, any surgery to the legs or pelvis, neurosurgery, major trauma, recent prolonged immobilization (within 2 weeks before screening, eg, due to trauma, surgery, or other illness markedly limiting mobility); is planning surgery requiring prolonged immobilization; or has a hereditary or acquired predisposition or elevated risk for venous or arterial thrombosis, such as Activated Protein C resistance, antithrombin-III-deficiency, protein C deficiency, protein S deficiency, hyperhomocysteinemia, or antiphospholipid antibodies (eg, anticardiolipin antibodies, lupus anticoagulant); or has thrombogenic cardiac valve or rhythm abnormalities of the heart associated with thromboembolism (eg, atrial fibrillation).

Note: Routine screening through laboratory tests for thrombophilia is not required. Exclusion from participation is based on reported medical history.

11. Has uncontrolled or severe hypertension (systolic blood pressure ≥ 160 mmHg or diastolic blood pressure ≥ 100 mmHg) at Screening (V1).

Note: if hypertension can be controlled with medications and is no longer severe at treatment allocation (V2), the participant may be eligible.

12. Has severe dyslipoproteinemia.

Note: Routine screening is not required. A lipid panel may be performed at V1 at the discretion of the Investigator.

13. Has a history of migraine with aura or focal neurological symptoms.

14. Has diabetes mellitus with end-organ involvement (nephropathy, retinopathy, neuropathy, or vascular involvement) or has diabetes for >20 years duration.

15. Has multiple cardiovascular risk factors such as obesity (BMI >30 kg/m²), inadequately controlled hypertension, use of tobacco/nicotine products, or inadequately controlled diabetes which, in the opinion of the Investigator, in composite pose an unacceptable risk of study participation.

Note: A participant who has a BMI >30 kg/m² **only** is not exclusionary. The Investigator should consider the severity of each risk factor in determining whether study participation is appropriate.

Gastrointestinal Disorders:

16. Has a history of pancreatitis associated with severe hypertriglyceridemia.

17. Has a presence or history of clinically significant liver disease, including active viral hepatitis or cirrhosis. Participants with a prior history of liver disease which is now inactive or successfully treated may be eligible if liver function values (ie, aspartate aminotransferase [AST], alanine aminotransferase [ALT], total bilirubin) have been normal for the past year and are within the normal range (per central laboratory) at V1. Liver function testing may be repeated once prior to V2 at the discretion of the Investigator if results are inconsistent with the participant's clinical status or recent laboratory results.

18. Has a history of malabsorptive surgical procedures (eg, Roux-en-Y gastric bypass, jeunoileal bypass, biliopancreatic diversion).

Other Medical Disorders:

19. Has a history of malignancy \leq 5 years before signing the informed consent except for adequately treated basal cell or squamous cell skin cancer.

Note: Participants with a history or presence of liver tumors (benign or malignant) or sex steroid-influenced malignancies (eg, genital organs, breasts) are excluded regardless of the interval since the history of the malignancy.

20. Has a history or presence of meningioma.

21. Has any disease that may worsen under hormonal treatment such as disturbances in the bile flow (presence of or history of cholestasis, presence of gallstones), systemic lupus erythematosus, pemphigoid gestationis or idiopathic icterus during a previous pregnancy, middle-ear deafness (otosclerosis), Sydenham chorea, or porphyria.

Note: History of cholecystectomy does not exclude a participant.

22. Has a current or previous history of medically diagnosed severe depression unless the potential participant is determined to be clinically stable and asymptomatic.

23. Has a known allergy/sensitivity or contraindication to NOMAC-E2.
24. Has a history (current or within the past 2 years) of drug or alcohol abuse or dependence.
25. Has any clinically relevant abnormal laboratory result at Screening (V1) as judged by the Investigator.
26. Has a history or current evidence of any condition, therapy, or other circumstance that in the opinion of the Investigator might confound the results of the study, affect participant's well-being, or interfere with the participant's participation for the full duration of the study (ie, approximately 1 year).

Prior/Concomitant Therapy

27. Has received any treatment listed in [Table 6](#) more recently than the "last allowable use" indicated in [Table 6](#) and/or needs to continue to receive any treatment listed in [Table 6](#).

Note: Contraceptives are allowed beginning the day following the last placebo tablet intake.

Prior/Concurrent Clinical Study Experience

28. Has used an investigational drug and/or participated in any other clinical study within 2 months before V2.

Other Exclusions

29. Is or has an immediate family member (eg, spouse, parent/legal guardian, sibling, or child) who is part of the investigational site or Sponsor staff directly involved with this study.

